Randomised trial comparing CPAP machines with reusable vs disposable circuits

STEERING COMMITTEE

Primary Investigator:

[name] [name], MS Ramaiah Medical College

Co-investigators:

[name] M, MS Ramaiah Medical College

[name] MV, MS Ramaiah Medical College

Other Guidance:

The Wellcome Trust Research Steering Group provided assistance and guidance with protocol design.

Members providing technical input included:

[name], Neonatologist, in the role of Consultant to the Wellcome Trust

[name], Consultant to MTTS

PARTICIPATING SITES

M.S. Ramaiah Medical College, Bangalore, Karnataka, India.

TRIAL CONTACT

[name] [name]

MS Ramaiah Medical College

Email: [contact]

[contact]

INSTITUTIONAL ETHICS COMMITTEE

[name] (Chairman)

Ethics Committee

M S Ramaiah Medical College and Hospitals

[name]

[name]

Email: [contact]; [contact]

[contact]

TRIAL SUMMARY

1. Aim & Hypothesis:

The study aims to assess the basic functionality of a newly designed CPAP machine with reusable circuits to existing machines with disposable circuits, for treatment of newborn infants diagnosed with respiratory distress syndrome. The assessment will compare a comprehensive list of physiological parameters over the first 72 hours of treatment, and will also monitor rates of side effects and adverse events. The null hypothesis is that infants treated on the two categories of machine (reusable vs disposable) will not differ in relation to key physiological parameters by more than 0.63 standard deviations.

2. **Background:**

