4.7. Trial funding

Funding is being provided through Thrive Networks, which is in receipt of funding from the Wellcome Trust under the R&D for Affordable Healthcare in India scheme. The purpose of this project, entitled “Continuous Positive Airway Pressure (CPAP) machine to promote rational oxygen use for neonates and to reduce the incidence of retinopathy of prematurity (ROP)” is to develop and commercialise a low-cost CPAP machine for the Indian marketplace.

5. Sample size and statistical analysis:

5.1. *Sample size calculation*

Sample size calculations are based on the primary outcomes. All the outcomes are selected to be continuously distributed. A sample size of 40 infants per group has been selected as something that is achievable at the anticipated recruitment rate at Ramaiah Hospital in the time available (10 months, including 8 months for recruitment at 10 randomised infants/month). The trial will cease when 40 infants have been randomised to each arm (i.e., at this point the other arm must have 40 or more randomised infants). With this sample size, a difference of 0.63 standard deviations is detectable, with 80% power ($1-\beta$) and a 5% false-positive rate (α). We lack data, within the study population, on the anticipated outcomes in the primary and secondary endpoints.

Feasibility: An assessment of eligible infants meeting the inclusion criteria (and none of the exclusion criteria) in February and March 2016 (two complete months) identified:

- 24 inborn neonates eligible for randomisation (i.e., 12/month); and
- 11 outborn neonates admitted to Ramaiah <6 hours of age (i.e., 5.5 /month).

This give a total of 17.5 eligible infants per month. Previous experience at Ramaiah is reported to be a 70% recruitment rate which, if maintained in the current study, would yield an average of 12.2 randomised infants/month. This is above the required randomisation rate of 10 infants per month, and suggests that the project would be feasible with a 60% recruitment rate.

5.2. *Statistical analysis*

Primary and selected secondary outcomes - descriptive: The raw values of the primary outcome (FiO_2) and five secondary outcomes (SpO_2 , respiratory rate, pH, PaO_2 , PaCO_2) will be graphed to allow visual comparison of differences at baseline and over time.

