Statistical Analysis Plan

“Randomised trial comparing CPAP machines with reusable vs disposable circuits”

Introduction

1. This document sets out the statistical analysis plan for a randomised trial conducted at Ramaiah Medical College hospital, Bangalore, Karnataka, India, between June 2017 and July 2018 (inclusive). At each point, the plan sets out the text in the original plan and highlights any variations from that plan, as updated on 31 August 2019.
2. **Limitations:** There were two important limitations to the study analysis as envisaged in the protocol:
 - a. The achieved sample size was n=51. This compares to the 80 randomised infants planned for as a feasible target in the setting, despite a 5-month extension to recruitment. The planned sample size was only capable of estimating a major difference (a difference of 0.70 standard deviations between the means) in the primary outcome. The achieved sample size therefore substantially reduces the study power.
 - b. Many of the outcomes, including the primary outcome, were predicated on the assumption that staff would be targeting oxygen saturations of 90-95%, as measured through pulse oximetry (SpO_2); it transpired that this was rarely the case. SpO_2 within the 90-95% target range was achieved in 54 of 224 readings (24.1%) overall, by reading:
 - 14 of 51 (27.5%) of readings at baseline;
 - 9 of 50 (18.0%) of readings at 6 hours;
 - 9 of 49 (18.4%) of readings at 12 hours;
 - 15 of 41 (36.6%) of readings at 24 hours;
 - 4 of 24 (16.7%) of readings at 48 hours; and
 - 3 of 9 (33.3%) of readings at 72 hours.

Exclusion of other outcomes SpO_2 was outside the target readings would have markedly reduced the sample size available, so analysis was continued as planned, including all records, with a note that the analysis may be contaminated. In the case of the primary outcome, for example, the analysis interprets the amount of oxygen required as being reflective of that needed to achieve targeted saturations; when the SpO_2 is above the target range, it is difficult to ascribe meaning to the oxygen level that was provided.

Primary outcome

3. **Descriptive analysis as specified in the protocol:**

Primary and selected secondary outcomes - descriptive: The raw values of the primary outcome (FiO_2) and five secondary outcomes (SpO_2 , respiratory rate, pH, PaO_2 , $PaCO_2$) will be graphed to allow visual comparison of differences at baseline and over time. [Protocol, para 5.2]

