4. **Descriptive analysis as revised:** No change.

5. **Planned analysis as described in the protocol:**

Primary outcome: With longitudinal measurement, the interpretation of later results can be impacted by differential losses before 72 hours (death or intubation and ventilation). Analysis will therefore commence with a Kaplan-Meier curve comparing ‘loss’ (death or intubation and ventilation), and an associated Cox regression model to compare the rate of loss in the

Statistical Analysis Plan

"Randomised trial comparing CPAP machines with reusable vs disposable circuits"

[figure not shown]
two treatment arms. The results of this survival analysis will provide the context within which the longitudinal results will be interpreted. If there are differential losses over time, the least affected time point will be 6 hours after treatment commencement, and this time point will be promoted to being the primary outcome. If losses over time are not differential, the planned analysis is described below.

The preferred omnibus analysis is a longitudinal mixed effects model (using PROC MIXED in SAS 9.4), controlling for baseline through a random 'intercept', in line with international recommendations for controls on baseline.^[30] Individual analyses at each time point (6, 12, 24, 48, and 72 hours) will be by multiple regression, again adjusting for baseline as a covariate.^[30] If multiple regression model requirements for normality and homoscedasticity are not met, analysis will be by t-test which is known to be robust to violations of the normality assumption, and will be based on the change in variable from baseline value, providing some control for different baselines, but without the additional control offered by multivariate analysis.

Where performed, multivariate analysis will control for stratification; if univariate analysis is used, separate stratum-specific sub-analysis will be undertaken, and a stratified t-test will be performed. Additional covariates will be adjusted for in multivariate analysis, if the baseline comparison shows substantial group difference in significant prognostic factors (e.g., onset of labour is associated with the stimulation of surfactant production, so analysis will control for mode of delivery if there is a clinically relevant mal-distribution). [Protocol, para 5.2]

6. Revisions to planned analysis:

- As noted above (para 2b), all data analysed, not just data where SpO₂ was 90-95%

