- Kaplan-Meier curve produced to assess treatment failure in the first 72 hours, with difference assessed by log-rank test. Three Dolphin and one Fisher-Paykel failure in first 72 hours; not statistically different by log-rank test, $p=0.30$. Two infants ceased CPAP and were discharged <72 hours (one left against medical advice, the other discharged home), and were excluded from the denominators from the point of discharge. No control for stratification in analysis, as no failures in the older gestational group.

Statistical Analysis Plan

“Randomised trial comparing CPAP machines with reusable vs disposable circuits”

- c. While the difference between groups was not statistically significant in survival analysis, change at in FiO₂ from baseline to 6 hours was preferred as the primary endpoint, given the small sample size. As the distribution was strongly peaked, a non-distributional test (Wilcoxon) was preferred, controlling for stratification (van Elteren's extension).

Secondary outcomes

7. Descriptive analysis as specified in the protocol:

Primary and selected secondary outcomes - descriptive: The raw values of the primary outcome (FiO₂) and five secondary outcomes (SpO₂, respiratory rate, pH, PaO₂, PaCO₂) will be graphed to allow visual comparison of differences at baseline and over time. [Protocol, para 5.2]

8. Descriptive analysis as revised: No change.

9. Analyses as specified in the protocol:

Secondary outcomes: Five of the secondary outcomes (SpO₂, respiratory rate, pH, PaO₂, PaCO₂) will be analysed using the same procedures as for the primary outcome. It is anticipated that the three arterial blood gases (pH, PaO₂, PaCO₂) will not be performed on all infants, particularly infants that recover rapidly; if so, this analysis will be restricted to change from baseline at the 6-hour reading.

Duration of CPAP (hours), for those not failing CPAP treatment, is the only continuous secondary outcome this is expected to be non-normally distributed and will therefore be assessed using Wilcoxon's rank sum test, with stratum-specific contributions aggregated using van Elteren's extension to the Wilcoxon test.^[31]

The remaining secondary outcomes are dichotomous and will be tabulated and compared using stratum-specific relative risks (RRs); the homogeneity of stratum-specific RRs will be assessed using Cochran's Q and the I² tests^[32]. [Protocol, para 5.2]

10. Revisions to planned analysis:

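### SAP 2a's 0.70 SD conflicts with the protocol's 0.63 SD for the same planned sample, the worded null carries a margin that no analysis tests, and no effect estimate is named beside the rank test

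*Protocol*

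**What the plan says.** - **Protocol, Trial Summary, 1. Aim & Hypothesis.** The null is that infants on the two categories of machine "will not differ in relation to key physiological parameters by more than 0.63 standard deviations".
- **Protocol 5.1.** Forty per arm was chosen because it could be recruited in the time available. "With this sample size, a difference of 0.63 standard deviations is detectable, with 80% power", with a 5% false-positive rate. No SD in FiO₂ units is given.
- **Protocol 5.2.** The planned comparisons are Cox regression for losses, a mixed model, baseline-adjusted regression at each time point (or a t-test on change from baseline if its assumptions fail), a stratified Wilcoxon test for CPAP duration, and relative risks. None carries a margin.
- **SAP 2a.** Recruitment reached 51 infants against 80 planned. The planned sample is described as "only capable of estimating a major difference (a difference of 0.70 standard deviations between the means) in the primary outcome", with no power, alpha or derivation. The text continues "The achieved sample size therefore substantially reduces the study power" and gives no figure for 51.
- **SAP 5, 6c and 10a.** Para 5 restates the protocol, in which each time point "will be by multiple regression, again adjusting for baseline as a covariate", together with the t-test fallback. Para 6c moves the primary endpoint to the 6-hour FiO₂ change: "As the distribution was strongly peaked, a non-distributional test (Wilcoxon) was preferred, controlling for stratification". Para 10a uses the same van Elteren test for SpO₂, respiratory rate and CPAP duration. Neither 6c nor 10a names an effect estimate or interval.
- **SAP 1.** The trial ran from June 2017 to July 2018, and the plan is given "as updated on 31 August 2019".

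**The concern.** One number, 0.63 SD, does two jobs. In section 5.1 it is what the sample can detect. In the hypothesis it is a tolerance that the null allows. These lead to different tests and different conclusions. The SAP then describes the same sample with a second number and gives no basis for it, so a reader cannot tell what the trial was built to find or how much was lost at 51 infants.

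The missing estimate matters because the study is meant to show that the new machine works acceptably beside existing ones. With 51 infants, the informative result is the range of differences that the data still allow. A van Elteren p-value does not show that range.

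**Working it through.** **Inputs.** 40 per arm, 80% power and 5% alpha (Protocol 5.1; sidedness is not stated, taken as two-sided). 0.70 SD and 51 infants (SAP 2a). 50 SpO₂ readings at 6 hours (SAP 2b: "9 of 50 (18.0%) of readings at 6 hours"), used as a guide to the FiO₂ count. The documents do not give achieved arm sizes, so the splits below are assumptions.

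**1. Reproduce 0.63 SD.** Normal approximation: n per arm = 2(1.960 + 0.842)²/d² = 15.70/0.63² = 39.6, so 40. In reverse, d = 2.802 × √(2/40) = 0.626 SD. By noncentral t, d = 0.634 SD, and power at 0.63 SD is 79.5%. The protocol's figure is right. One-sided 5% does not fit (0.556 SD).

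**2. Try to reproduce 0.70 SD.** At the protocol's power and alpha, n = 15.70/0.70² = 32.04, so 33 per arm, not 40.

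| Possible source of 0.70 SD | Result |
|---|---|
| 40 per arm, two-sided 5% | power 87.1% (t), 87.9% (normal) |
| 33 per arm, 80% power, two-sided 5% | 0.700 SD (t) |
| 40 per arm, 80% power, two-sided 2.5% | 0.701 SD (t), 0.689 SD (normal) |
| Wilcoxon, normal data, 40 per arm | 0.634/√0.955 = 0.649 SD |
| Wilcoxon, worst-case efficiency, 40 per arm | 0.634/√0.864 = 0.682 SD |
| 95% CI half-width, 40 per arm | 0.445 SD |
| Achieved 51, split 25/26 | 0.801 SD |

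Only the first three rows reach 0.70, and each needs an input that neither document states. Use of the rank test does not explain it, and it is not the achieved-sample figure.

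**3. What 51 infants can detect** (80% power, two-sided 5%, noncentral t): 0.80 SD at 25/26, 0.82 SD at 20/31, and 0.81 SD at 25/25 if 50 infants have a 6-hour value. Power for 0.63 SD falls from 79.5% at 40/40 to 59.7% at 25/26. The 95% CI half-width grows from 0.445 SD as planned to 0.563 SD at 25/26 or 0.569 SD at 25/25.

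**4. Worded null against tested null, at 40 per arm.** A test of no difference is significant once the observed difference passes about 1.96 × √(2/40) = 0.44 SD. A test of the null as worded would need roughly 0.63 + 1.645 × √(2/40) = 1.00 SD. An observed difference of, say, 0.5 SD would therefore be significant in the planned analyses while lying inside what the stated null permits.

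**5. Estimates.** The mixed model, regression and t-test restated in SAP 5 all give an effect size. SAP 6c makes the rank test preferred and neither withdraws nor confirms them. SAP 5 itself also switches from regression to a t-test when model assumptions fail, and 6c reports a strongly peaked distribution. A reader cannot tell which estimate, if any, will accompany the primary p-value.

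**The case against.** The best defence is that these are slips in wording. Section 5.1 states the design basis correctly, section 5.2 plans ordinary difference analyses, and the 0.70 sits in a limitations paragraph and drives nothing. The SAP also says that it lists variations from the plan, so text it does not vary still stands. Para 5's estimate-producing analyses would then remain, with van Elteren added only to judge significance, and the graphs of raw values are kept. The SAP openly admits reduced power, and para 11 calls the study exploratory.

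Most of this stands. It limits the estimate question to an ambiguity. It does not reconcile 0.63 with 0.70, and it does not supply the margin that the worded null implies.

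A further objection also stands: an interval for FiO₂ is hard to interpret. Only 9 of 50 SpO₂ readings at 6 hours were in the target range, and SAP 2b itself warns that the oxygen level given means little when saturation is above target.

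Two stronger readings are tempting, and the documents support neither.
- **An equivalence or non-inferiority trial that will treat non-significance as comparability.** The arithmetic alone cannot rule out non-inferiority, because a 0.63 SD margin at one-sided 2.5% also gives 40 per arm. But section 5.1 speaks of a detectable difference, no analysis carries a margin, SAP 11 says that the sample was set by recruitment time and not by a pre-set clinically significant difference, and neither document says that non-significance will be read as comparability. For illustration only: an equivalence test with that margin, one-sided 5% tests and no true difference would have about 75% power at 40/40 and 43% at 25/26.
- **The SAP has dropped effect estimates altogether.** It has not said so.

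**Conclusion.** The point holds as two errors of statement and one ambiguity.
- SAP 2a's 0.70 SD is inconsistent with Protocol 5.1. The planned sample detects 0.63 SD on the stated inputs, and the achieved sample about 0.80 SD.
- The null in the Aim & Hypothesis is not the null that any planned comparison tests.
- SAP 6c and 10a leave unclear which effect size accompanies the rank test. This is secondary, and it is not shown to be an omission.

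No test or sample size changes. What is at stake is whether a reader can judge what 51 infants do and do not exclude. The 0.63 SD result assumes two-sided 5%. The figures for 51 assume normal data and the arm splits shown, moving only between 0.80 and 0.82 SD across those splits.

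**What to change.** Make the changes in the SAP and label them post hoc, because it was updated after the trial had run and already reports outcome data.

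1. In 2a, replace 0.70 with 0.63 SD, or state the power and alpha behind 0.70. Add the detectable difference for the 51 infants from the actual arm sizes.
2. State the null as no difference between machines. Keep 0.63 SD only as the detectable difference at 40 per arm.
3. Keep van Elteren. Beside it, for the 6-hour changes in FiO₂, SpO₂ and respiratory rate and for CPAP duration, name one stratified estimate with a 95% CI for each outcome, in natural units. The stratified Hodges-Lehmann shift matches the rank test and serves all four. For the three 6-hour changes, the stratified mean difference in change from baseline, in line with the protocol's own fallback, is a reasonable alternative. Either can be defended; what matters is that one is named and does not switch with the data.
4. Report the FiO₂ interval with the SAP 2b caveat, and state that non-significance will not be read as comparability.

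The cost is two wording corrections, one added figure and four intervals from data already held. The downsides are that the result may read as inconclusive, and that a mean-based interval can disagree with the rank p-value in a borderline case. If a mean difference is chosen, show both.

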2.1. Plain language summary

One of the commonest sources of serious newborn morbidity and mortality is difficulty with breathing. When this occurs, three main types of supportive therapy are available to increase the provision of oxygen to cells: a) passive provision of oxygen-enriched gases (i.e., higher than the 21% O₂ found in the earth's atmosphere) through tubes in the nostrils, or by putting a hood over the baby's head and enriching the gases under that hood; b) provision of room air or oxygen-enriched gasses under pressure, frequently performed using a method called continuous positive airway pressure [CPAP] therapy; and/or c) by using a machine that is able to breath on behalf of the baby, most commonly referred to as mechanical ventilation [MV].

Passive therapy is the least invasive method but is also of limited benefit, particularly for infants born preterm. CPAP is more effective than passive methods because continuous distending pressure to the lungs allows better oxygen exchange; however, the distending pressure increases the risk of damage to the lung. MV is the only method that can be used on babies without a neurological impulse to breath, but the mechanical breathing action can damage the lungs, and MV is usually provided through a tube inserted into the lungs which increases the risk of lung infection; MV machines are also significantly more expensive than CPAP machines.

In high resource settings, CPAP is now the preferred method of providing oxygen for infants where passive therapy is insufficient, because of the lower infection risk, lower risk of lung damage, and relative ease of clinical care. CPAP is increasingly recommended for low resource settings, but the CPAP machines used in high resource settings are too expensive for low resource settings due to high-priced consumables (\$US50-200/baby), and are usually unusable in low resource settings because they require 'medical air' (clean air in a cylinder, or through a piped wall system) with which to blend 100% oxygen. Low cost 'indigenous' machines ('jury-rigged' by hospital staff) have also been developed, but these do not provide the heated, humidified and blended gasses, that are recommended for CPAP.

This study seeks to evaluate a novel CPAP machine that provides heated, humidified, blended gasses, in line with recommendations for high-resource settings, while massively reducing costs by including re-usable tube sets and humidifiers that can be autoclaved, and with an on-board air-compressor to allow use in a broader range of clinical settings. By reducing the cost per CPAP treatment, such a machine can dramatically increase the number of hospitals in low resource settings that can provide high quality CPAP treatment.

2.2. Literature review

Neonatal deaths (0-27 days of age) were estimated to account for 40% of all deaths under five years of age in 2010.^[1] Preterm birth complications are the largest single cause of neonatal mortality, accounting for three in every eight neonatal deaths in 2010.^[2] As other causes of child mortality such as tetanus, diarrhoea and pneumonia are addressed, it becomes increasingly urgent that prevention and treatment programs address complications of preterm birth, if we are to continue to reduce child mortality in low resource settings.

The basic bilateral structure of the lungs develops through the embryonic stage (4-7 weeks of gestation) and then proceeds with the formation of the basic vascular structure, ending at around 24 weeks of gestation. From 24-36 weeks' gestation, basic alveoli are formed for gas exchange, increasing the surface area over time, and related cells commence producing surfactant. At around 36 weeks' gestation the final stage of lung development commences, with rapid growth in the number of alveoli; this stage continues in the postnatal period.^[3]

[figure not shown]
Preterm birth disrupts this process and often leads to poor lung development with permanently impaired lung function. Surfactant, which is detectable by 24 weeks of intrauterine life,^[4] reduces surface tension in the lung, preventing lung collapse, and reducing the work of breathing and increasing lung compliance.^[5] Neonatal Respiratory Distress Syndrome (RDS) is a direct result of pulmonary immaturity and surfactant deficiency:^[5] the incidence of RDS increases sharply with *decreasing* gestational age,^[6] such that the majority of liveborn babies <32 weeks gestation develop RDS.^[7] The case fatality rate of infants with RDS also increases with decreasing gestation, indicating more severe disease at lower gestations.

RDS can be prevented and/or reduced in severity by accelerating fetal lung maturation through use of antenatal corticosteroids,^[8] by permitting the onset of labour which stimulates surfactant production,^[6] and by postnatal administration of exogenous surfactant.^[9] Although use of antenatal corticosteroids is promoted in low resource settings, the evidence shows that its use is rare in these settings;^[7] and exogenous surfactant is too expensive for routine use in low resource settings^[10]. Even if all of these interventions could be implemented fully, however, there would still remain a group of infants with RDS who would need supportive therapy.

The use of CPAP to treat RDS was first reported in 1971.^[11] While many different methods of providing CPAP are available, a common combination uses short binasal prongs as an interface to deliver heated and humidified gases, blending oxygen and air to achieve the desired amount of oxygen enrichment; a typical configuration is shown in Figure 1. Pressure can be delivered in a variety of ways, but is commonly delivered in the fashion shown in Figure 1, by submerging an expiratory tube in water to provide a distending pressure determined by the depth of insertion; this 'bubble CPAP' is increasingly popular as it is relatively easy to manage and because the bubbling of the water in the expiratory circuit results in high frequency oscillations in the lungs which may result in more efficient gas exchange.^[12] The new and existing CPAP machines to be compared in the current study are bubble CPAP devices.

Cochrane reviews of randomised trials in high resource settings have demonstrated that CPAP can reduce the need for intubation^[13] and reduce re-intubation of infants being weaned from MV.^[14] More recently, separate meta-analyses have demonstrated that CPAP can be used in the delivery room^[15] or at any stage prior to intubation^[16] to reduce the use of MV and thereby prevent the chronic lung disease associated with MV.

Figure 1: Schematic diagram of a 'bubble' CPAP circuit^[17]

A recent review of changes in mortality over time in the USA found that the most rapid reduction in RDS mortality coincided with the introduction of CPAP and argues, on that basis, for the roll-out of CPAP to treat RDS in low-resource settings^[18]. A separate review of studies of CPAP in low resource settings found consistent evidence of benefit in avoiding MV^[19], and a related editorial proposes that CPAP should be promoted as the standard of care for RDS in low resource settings.^[20]

The accumulated evidence of the value of CPAP is reflected in its inclusion in the list of Essential Interventions, Commodities and Guidelines for Reproductive, Maternal, Newborn and Child Health by the Partnership for Maternal, Newborn & Child Health^[21], which includes the World Health Organization. Indian clinicians have recognised the value of CPAP for treating RDS for more than a decade^[22, 23], and have more recently concluded that surfactant is prohibitively priced, relegating it to the status of a salvage therapy where CPAP fails^[10].

The recent establishment of a nationwide infrastructure of Level II Special Care Newborn Units (SCNUs) funded by the National Rural Health Mission has created a structural opportunity to roll-out a high quality CPAP program. A recent estimate suggest that up to half a million Indian newborns will require CPAP each year^[24] but, as with surfactant, the capacity to satisfy this demand will be dependent on price. If state of the art disposable tubes and humidifiers cost \$US100 each, this would imply an annual consumable cost of over \$US50 million, without taking into account the capital cost of acquisition.

The March of Dimes Global Action Report on Preterm Birth notes that there is a need for innovation to create robust low cost CPAP for use in low resource settings^[7]. While bubble CPAP machines in high-resource settings routinely cost around \$US6,000 to purchase, a recent project has built a simple bubble CPAP machine with an estimated cost of goods of \$US350.^[25] Unlike homemade bubble CPAP machines, this machine allows blending of air and oxygen, but does not allow humidification and heating of the inspired gases; the cost per treated patient on such a machine is not as yet known.

As the current standard of care includes use of humidified and heated gases during treatment with neonatal CPAP,^[26] it is not envisaged that the Indian public health system or private health providers will adopt these minimal-function devices, and it is not clear if they provide superior outcomes to existing 'indigenous' CPAP machines. The current study seeks therefore to compare a fully-functional bubble CPAP system with a dramatically lower cost per CPAP-treated neonate, achieved by reducing the number and cost of consumables, with state of the art CPAP machines. The current study will seek to compare, by randomised controlled trial, physiological indices indicative of the quality of respiratory support provided to demonstrate the basic functionality of the new CPAP machine with re-usable tube sets and humidifiers in comparison to current state of the art machines using consumables. Similar methods^[27, 28] and outcomes^[27-29] have previously been used to compare alternative methods of providing CPAP.

3. **Design:**

3.1. ***Patient selection criteria***

Inclusion criteria: The following groups of infants will be considered eligible:

- a) Infants born at the hospital ('inborn infants') or born elsewhere, and admitted to Ramaiah hospital under 6 hours of age;
- b) Infants with a gestational age at birth (weeks ^{+days}) in the range $\geq 28^{+0}$ to $\leq 36^{+6}$;
- c) Infants thought to have RDS (clinically diagnosed after onset of respiratory distress <6 hours of age, sometimes confirmed by X-ray showing homogenous bilateral opacity) who would routinely be provided CPAP; and
- d) Infants <24 hours old at the time of fulfilling other inclusion criteria.

Exclusion criteria: The following groups of infants will be excluded to avoid any accidental imbalance in rare conditions between groups post-randomisation:

- a) Infants with a 1-minute Apgar score <3 (as a marker of severe birth asphyxia);
- b) Infants who received MV prior to randomisation;
- c) Infants with suspected meconium aspiration syndrome will be excluded to avoid any imbalance in this condition across groups;
- d) Infants clinically suspected to have another specified serious condition as their main disease process, ***diagnosed prior to randomisation***, specifically: cardiac anomaly, other congenital malformation with respiratory sequelae, septicaemia, pulmonary haemorrhage, pneumothorax, meningitis, poor respiratory effort or recurrent apnoea, or brain haemorrhage (IVH Grades III or IV);
- e) Infants who have an airway abnormality precluding the use of the standard CPAP interface proposed for this study (e.g., Pierre-Robin sequence, cleft lip or cleft palate) or who have a neuromuscular condition that interferes with respiration;
- f) Any infant whose treating clinician believes should not be randomised due to some other condition, or for any other reason (reason to be documented).

3.2. ***Primary outcome***

The primary outcome will be a comparison of fraction of inspired oxygen (FiO₂), measured as a change from baseline at 6, 12, 24, 48 and 72 hours after treatment commencement.

3.3. ***Secondary outcomes***

A range of secondary outcomes will be assessed:

- Oxygen saturation by pulse oximetry (SpO₂), measured as a change from baseline at 6, 12, 24, 48 and 72 hours after treatment commencement;
- Respiratory rate (breaths/minute), measured as a change from baseline at 6, 12, 24, 48 and 72 hours after treatment commencement;
- Arterial blood gas analyses, measured as a change from baseline at 6, 12, 24, 48 and 72 hours after treatment commencement, including:
 - pH;
 - Partial pressure of oxygen (PaO₂); and
 - Partial pressure of carbon dioxide (PaCO₂).
- CPAP failure (death or need for intubation and mechanical ventilation as demonstrated by an FiO₂ requirement $\geq 60\%$ for ≥ 1 hour to maintain SpO₂ at 90-95%);

- Surfactant provided when $\text{FiO}_2 > 40\%$ to maintain SpO_2 at 90-95% for ≥ 30 minutes, with RDS confirmed by chest X-Ray, in line with current Ramaiah standard practice;
- An omnibus indicator comprising CPAP failure or surfactant provision;
- Duration of CPAP treatment (hours) in infants that do not fail CPAP;
- Selected complications of treatment will be evaluated as sentinel outcomes. These, include:
 - Damage to the nasal septum;
 - Damage to the nares;
 - Pneumothorax as diagnosed by X-ray;
 - Intra-ventricular haemorrhage (IVH), intra-cranial haemorrhage (ICH), or periventricular leukomalacia (PVL) as diagnosed by cranial ultrasound scan;
 - $\text{FiO}_2 \geq 60\%$ to maintain SpO_2 at 90-95% for one hour or more, during CPAP treatment;
 - Intubation and mechanical ventilation;
 - For infants born at 28^{+0} to 33^{+6} weeks' gestation, oxygen dependent at 36 weeks' gestation; and
 - Death prior to hospital discharge.
- A Serious adverse Event (SAEs) is any untoward medial occurrence that:
 - Results in death;
 - Is life-threatening;
NOTE: the term “life-threatening” in the definition of “serious” refers to an event in which the patient was at risk of death at the time of the event; it does not refer to an event which hypothetically might have caused death if it were more severe.
 - Requires inpatient hospitalisation or prolongation of existing hospitalisation;
 - Results in persistent or significant disability/incapacity, or
 - Is a congenital anomaly/birth defect

4. **Procedures:**

4.1. ***Recruitment***

Inborn infants: If preterm delivery is imminent, obstetric staff and/or their pediatric counterparts will inform parents that their baby may be eligible for the study, and will provide an information sheet pre-approved by the Ramaiah Medical College and Hospitals Ethics Committee, to give them additional time to consider whether they wish to consent. Pre-consent can be provided at this time, with randomisation to follow only if the infant meets all the inclusion criteria and none of the exclusion criteria. If pre-consent has not been sought, once a baby is born and deemed to meet all inclusion criteria, and does not meet any exclusion criterion, trained pediatric staff will approach the parents to seek informed consent.

Outborn infants admitted to Ramaiah <6 hours of age: The parents of outborn infants likely to be eligible can be approached by the Ramaiah transfer team to seek pre-consent at the referring hospital, with randomisation to follow only if the infant meets all inclusion criteria and none of the exclusion criteria. If pre-consent has not been gained and a parent is available at the time an infant meets all inclusion criteria, and none of the exclusion criteria, trained pediatric staff will approach the parent(s) to seek informed consent.

Information sheets and consent forms: An information sheet and consent forms approved by the Ramaiah Medical College and Hospitals Ethics Committee will be used during the recruitment process.

4.2. ***Randomisation***

Block randomisation with variable block sizes will be used within each of two gestational age strata: $28^{+0}-33^{+6}$ weeks' gestation and $34^{+0}-36^{+6}$ weeks' gestation. These gestational age strata are chosen to reduce the possibility of a chance imbalance in gestational ages between the intervention and controls groups, post-randomisation, as the severity of RDS is inversely related to gestation. Infants of multiple births, of which more than one infant are eligible, will be randomised individually.

The order of the block sizes (4, 6, or 8) will be randomly selected and the assignment of will be random within each block, until the selection is forced. Random numbers will be generated by SAS 9.4 using randomly selected seed numbers; the seed will be selected by opening a large book and choosing left or right page by coin toss (heads=right).

Ramaiah hospitals will be provided with consecutively numbered, sealed opaque randomisation envelopes containing the assigned treatments: the two gestational strata will be differentiated using different colours. The envelope will be opened after written consent has been obtained and the infant has become eligible for the trial, and the assigned treatment will be immediately applied to the infant.

The randomisation procedure is as follows:

- a) Ensure that one machine of each type (FP/Dolphin) is available for use within 10 minutes;
- b) Confirm that the infant meets ALL inclusion criteria;
- c) Confirm that infant does NOT meet ANY exclusion criterion; and
- d) Confirm that informed consent has been received.

If all of the steps are confirmed, the infant's gestational group is identified, to determine the correct stratum, and the next randomisation envelope for that infant will be opened.

4.3. ***Blinding***

Blinding of intervention is not possible, as the machines are visibly different. Some blinding of outcomes assessment will be performed – see item 4.5 Measurement of Outcomes.

